previous study suggested that low PiMax (both airway (aPiMax) and esophageal (ePiMax)) measured during airway occlusion while the child is breathing spontaneously, was associated with re-intubation.⁶⁵ A trained provider (research respiratory therapist or study PI) performed airway occlusion maneuvers to measure both aPiMax and ePiMax, ensuring that the child was at end-exhalation and that the airway remained occluded for at minimum 3 consecutive breaths, but most of the time at least 5,⁵⁷ just before extubation. Measures of respiratory system capacity were obtained prior to extubation during airway occlusion, and measures of respiratory effort were obtained

both before and after extubation. Of the 409 patients, 34 were re-intubated within 48 hours (8.3%). Prior to extubation, re-intubation risk factors included lower aPiMax, and longer length of ventilation. After extubation, post-extubation upper airway obstruction (UAO), high respiratory effort or load (Pressure Rate Product (PRP), Pressure Time Product (PTP), Tension Time Index (TTI)) and high Phase Angle (PA) were associated with re-intubation. Because patients in this study had already passed SBTs, they generally had near normal compliance (low load), so pre-extubation respiratory effort was not associated with re-intubation. When looking specifically at measures of respiratory muscle capacity prior to extubation, there was a dose response relationship between lower aPiMax and re-intubation risk (Figure 3). Children with aPiMax ≤ 30 cmH₂O accounted for 33% of all extubated patients, but were responsible for 56% of all failed extubations (19/34). Thus, aPiMax alone is a marker of re-intubation risk (AUC 0.66 (0.57, 0.75)).

[figure not shown]

Figure 4: When children with low aPiMax develop high respiratory load (such as from post extubation UAO), they have very high re-intubation rates. Solid line is population average.

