Secondary Outcomes for SA 1: The 28 and 60 Day Ventilator Free Days (28D VFD, 60D VFD) will be secondary outcomes of this aim. Groups for VFD analysis will be based on any exposure to the intervention (acute or weaning) because some patients will never undergo a weaning phase randomization (i.e. died or were extubated right after the acute phase). If patients who died as well as those who dropped out are included in the VFD analysis, with the assumptions above regarding expected passing rate of SBTs, the estimated distribution of patients in 3 distinct groups will be: (a) REDvent only (n=108); (b) REDvent and control (n=90); (c) control only (n=102). We anticipate children in the REDvent only arm will have the most 28 D VFDs (anticipation 22), and those in the control only arm the least (anticipation 20). Directly comparing control only patients to REDvent only patients, with an expected standard deviation for VFDs between 5 to 9 days, we will be able to detect a 2-day change in VFDs between groups with a power between 0.35 and 0.82. Re-intubation rates are expected to be 10%, allowing us to confirm that REDvent is not inferior to usual care in regards to re-intubation with a non-inferiority margin of 0.10 with a power of 0.8 and alpha of 0.05. Finally, to ensure that REDvent is promoting greater patient effort of breathing and that the intervention does not alter clinical practice in the usual care arm, we will compare time weighted average values for direct measures of patient effort of breathing (PRP, PTP, Diaphragm Contractile Activity), and ventilator settings between intervention and control groups, and monitor the separation between groups over the time of the study.

D.6.4.2 SA2 Analysis Plan: To determine if changes to direct measures of respiratory muscle strength, load, effort, and architecture throughout the duration of MV are related to weaning outcomes.

Analysis and Sample Size: The primary outcome of this aim is weaning duration (as defined above). For this analysis, we will compare how each respiratory measure detailed in the data collection table relates to weaning duration. For respiratory muscle

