The revised milestone accrual plan has been reviewed and approved by the DSMB and NHLBI. Initial estimates of mortality and attrition were 13% and 7%, respectively, allowing for 20% of patients not meeting the primary outcome measure. Based on enrolled patients as of 08/16/2019, no patients have withdrawn from the study, and the overall mortality is 11.8%. As a result, the overall sample size estimate has been revised using 13% of patients who will not meet the primary outcome, rather than 20%. Target study enrollment of 300 total patients has been dropped to 276. The A-priori determination of 240 patients meeting the primary outcome measure has not changed.

[figure not shown]

Figure 8: Revised Milestone Accrual Plan

E Human Subjects Considerations

E1 Ethical Considerations

The human subjects for this study are infants and children who are intubated and mechanically ventilated in intensive care unit. It is anticipated that 276 intubated children will be enrolled in the study. The age of children will range from one month (\geq 44 weeks Post Conceptual Age) to 21 years. All participants enrolled in the study will be critically ill, requiring mechanical ventilation through an endotracheal or tracheal tube. The main risk of participation in this study is the placement of an esophageal catheter for measurements of esophageal pressure. While esophageal catheters (or nasogastric feeding tubes) are routinely used in children who are mechanically ventilated (it is the norm for all endotracheally intubated children to have a feeding tube, either nasogastric, orogastric, gastric, or jejunal), because this additional catheter is part of the research protocol, it is likely to be considered greater than minimal risk. However the study does provide potential for significant benefit for the patient, and as such the benefits generally outweigh the risks. Use of this catheter has been approved on multiple occasions with appropriate informed consent. The ultrasound measurements and RIP bands are non-invasive and pose minimal risk to the patient. There are no known risks associated with the use of volumetric capnography.

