Univariable analysis will focus on the relationship between the PVA variables above and clinical and mechanistic outcomes. Nearly all the variables of interest are continuous, so analyses will focus on strength of association and dose response. Nonparametric or parametric correlations will explore the relationships between continuous variables. The primary clinical outcome of length of ventilation after the first day of spontaneous breathing will be modelled with a competing risk regression to look at time to extubation against the competing risk of death. This type of model is necessary rather than traditional survival analysis or linear regression because both death and prolonged ventilation are undesired outcomes, and some proportion of children (likely 5-10%) will die even after the first day of spontaneous breathing. We have successfully used this framework in previous investigations.⁶⁸⁻⁷² We will then add in variables which may confound the relationship between PVA and clinical outcomes including demographic factors (age, co-morbidities), severity of initial lung injury, diagnostic data and medications. Similar analyses will be repeated all clinical and mechanistic outcomes. For mechanistic analysis (table 2), within each of the proposed mechanisms (VILI, VIDD, Delirium), the variable with the strongest association with PVA (or its subtype) will be included as the outcome variable.

Specific Aim 3) To develop and test a clinical decision support system using machine learning techniques to automatically identify common forms of PVA in children.

Hypothesis: (a) Machine learning models using waveforms available on all mechanical ventilators will accurately identify PVA subtypes compared to gold standard annotations which include measures of neural drive. (b) Algorithms can be optimized for high sensitivity and low false alert rates to identify children with frequent PVA.

Preliminary Data

Machine learning methods can detect DC breaths and the PVA subtypes leading to DC. We have been developing a machine learning framework using Spectral Analysis with a Convolutional Neural Network to detect PVA subtypes. Details about the methods used (and intend to employ here) are described below. Preliminary models were trained on 34, validated on 13 and tested on 18 patients from the REDvent dataset.

[figure not shown]

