Model assumptions and fit for multiple linear regression (with or without log transformation) will be assessed visually for normality of residuals as well as variance inflation factor and difference in betas (DFBETAS) for influential points. Model fit for binary multiple logistic regression will be assessed with Pearson Chi-square and deviance. Firth's penalized likelihood method will be used in subgroup analyses when event rates are small to reduce bias in the parameter estimates.⁴ When using negative binomial regression, model fit will be assessed for over and underdispersion with the scaled Pearson Chi-square/deviance and influential points assessed as previously described. The proportional hazards assumption will be assessed when using Cox proportional hazards modeling using graphical approaches ("log-log" figures and Kaplan-Meier curves) for each covariate. Repeated measures analysis for ventilator settings, lung mechanics, and respiratory measures will be assessed with linear mixed models and generalized linear mixed models that include a variable for time from randomization to control for correlation of values within each patient using the first-order autoregressive structure. The robust sandwich estimators for standard errors will be used to reduce heteroscedasticity when appropriate.

A detailed outline of each outcome's analysis approach to control for blocking variables and confounders is given in the Table 1. Pre-specified comparisons of interest are REDvent acute vs. usual care acute, REDvent weaning vs. usual care weaning, and four group combination: 1) REDvent acute + REDvent weaning 2) REDvent acute + usual care weaning 3) Usual care acute + usual care weaning 4) usual care acute + REDvent weaning. The four group combinations comparisons are exploratory and will only be considered if there are noted differences between both acute and weaning phase interventions.

October 2019- new milestone accrual plan

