Received Non-invasive respiratory support (NRS) post-extubation (secondary outcome)	Yes/no binary variable for receiving NRS after successful extubation. NRS includes: High Flow Nasal Cannula (HFNC) or nasal-only modes of non-invasive ventilation (CPAP or Nasal IMV or BiPAP) Successful extubation is defined as no death or re-intubation within 24 hours of extubation.	Patients who die within 24 hours of IMV or remain on IMV at 90 days are not included.	Multivariable logistic regression controlling for blocking variables and confounders.	Adjusted odds ratio for receiving NRS post-extubation with 95% C.I. for REDvent vs. Usual care will be presented.	January 2024 added as necessary component to interpret length of NRS after extubation more appropriately.
NRS duration after extubation (secondary outcome)	Duration of NRS after extubation is defined as the number of days and hours that the patient is on NRS after successful liberation. End of NRS is defined as absent continuously for at least 24 hours. Successful extubation is defined as no death or re-intubation within 24 hours of extubation.	Patients who die within 24 hours of IMV or who never receive NRS post-extubation are excluded. Patients who remain on NRS at 90 days will have 90 days imputed. Patients who die while on NRS will have their death date as end of NIV duration.	Log transformed multiple linear regression controlling for blocking variables and confounders.	NRS duration will be expressed in days. Adjusted mean difference and 95% C.I. for REDvent vs. usual care will be back transformed with $\exp(\text{estimate})$ and interpreted as a relative change.	None
Re-intubation within 48 hours of extubation (secondary outcome)	Binary variable for re-insertion of endotracheal tube within 48 hours of initial extubation.	Patients who remain on IMV for their index intubation or die within 48 hours of index extubation are excluded.	Multivariable logistic regression for the event re-intubation = yes. Adjusting for blocking variables and confounders.	Binary yes/no variable. Adjusted odds ratio for re-intubation with 95% C.I. for REDvent vs. Usual care will be presented.	None

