Negative Binomial Model	Length of Weaning (initial plan- revised); Ventilator Free Days	Count variables with adjustment for blocking variables and confounders. Model assumptions and methods to evaluate model fit: Pearson Chi-square/deviance for over and under-dispersion, DFBETAS and variance inflation factor.	Raw estimate and 95% C.I. for REDvent vs. usual care exponentiated to obtain Incidence Rate Ratio with 95% C.I. Patients in the REDvent group had a decreased rate of length of weaning by x% compared to usual care after adjusting for blocking variables and confounders.
Logistic regression	First SBT success; re-intubation, NIV/NRS use post extubation; ICU and 90 day mortality; decline in PCPC or POPC;	Binary outcomes with adjustment for blocking variables and confounders. Firth's penalized likelihood method was used in subgroup analyses when event rates were small to reduce bias in the parameter estimates.	Odds Ratio with 95% C.I. Patients in the REDvent group had higher odds (if OR>1) of achieving the outcome than usual care after adjustment for blocking and confounding variables.
Linear Regression	Days to first SBT and SBT passage; length of IMV; length of NRS/NIV post extubation; ICU Length of Stay; Hospital Length of Stay	Continuous outcomes with adjustment for blocking variables and confounders. Residuals evaluated for normality, homoscedasticity. DFBETAS and variance inflation factors assessed for influence of observations. Log transformation of the outcome used when appropriate.	Relative change (slope) of regression coefficient with 95% confidence interval. Patients in the REDvent group had a reduction in length of IMV by x compared to usual care. If log transformation used the estimate for the adjusted mean difference and 95% C.I. on the log scale were exponentiated. Outcome decreased by x% in the REDvent group compared to usual care.

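### Firth's penalised likelihood is confined to subgroup analyses, although the main re-intubation and mortality models are also sparse; extending it is a cheap improvement

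*Combined protocol and SAP*

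**What the plan says.** The model-fit paragraph of the final SAP (July 2024) states that Firth's "penalized likelihood method will be used in subgroup analyses when event rates are small to reduce bias in the parameter estimates". The logistic row of its Table 2 repeats the restriction in the past tense: the "penalized likelihood method was used in subgroup analyses when event rates were small to reduce bias in the parameter estimates". No subgroup is defined for this purpose.

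That same row lists the outcomes handled by logistic regression: "First SBT success; re-intubation, NIV/NRS use post extubation; ICU and 90 day mortality; decline in PCPC or POPC". In Table 1, re-intubation within 48 hours is "Multivariable logistic regression for the event re-intubation = yes" with adjustment for blocking variables and confounders. ICU and 90-day mortality have the same form. The changes column reads none for all three.

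REDvent-weaning against usual care is one of the pre-specified comparisons, so it is not a subgroup. Chi-squared or Fisher's exact tests are allowed for categorical data, but unadjusted results only summarise the data, and every primary and secondary outcome is to be presented adjusted. The SAP gives no expected event count for these models and no rule for separation.

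**The concern.** The SAP recognises small-sample bias in logistic regression and names a remedy, but applies it only to subgroups. If the main re-intubation and mortality models have few events per slope, the same reasoning covers them.

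Two things are at stake. Maximum likelihood estimates of a real effect lie somewhat too far from 1. If a covariate level or an arm has no events, a coefficient has no finite estimate, and the plan does not say what to do then. A change of covariates or method would have to be made with the data in view. These outcomes bear on safety, so a rule stated in the SAP is preferable.

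**Working it through.** **Denominators, reproducing the plan's figures first.**
- 276 enrolled less 13%: 276 × 0.87 = 240. With 25% passing the first SBT, 240 × 0.75 = 180. Both match the plan.
- The January 2023 minimum: 230 × 0.87 = 200, and 200 × 0.75 = 150.

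**The protocol's own yardstick.**
- D.6.4.3 allows 9 variables for at least 80 events: 80 / 9 = 8.9 events per variable.
- D.6.4.2 allows 20 variables for 240 × 0.9 = 216 SBT passers: 216 / 20 = 10.8.

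**Rates.**
- Re-intubation: 8.3% (earlier cohort, B.3.5) to 10% (D.6.4.1).
- Mortality: 11.8% observed overall by August 2019 (D10) to 12%. The 12% in D.6.4.1 is for deaths before the first SBT and is used here as a stand-in for the total.
- Weaning-phase deaths: no document gives a rate. The nearest figure is in section H (Asynchrony Aim 2, Hypothesis B), that "some proportion of children (likely 5-10%) will die even after the first day of spontaneous breathing". Applying it to children who failed a first SBT is an assumption.

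**Slopes.**
- Acute: arm 1, age 2, immunosuppression 1, oxygenation index 1, giving 5.
- Weaning: arm 1, acute group 1, age 2, oxygenation index 1, giving 5, or 6 if immunosuppression is included. The SAP is ambiguous on that.
- Oxygenation index is named as the confounder only for PiMax. Its use in these models is inferred.

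**Events = n × rate, and events per slope.**

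| Model | Low | High | Events per slope |
|---|---|---|---|
| Acute, re-intubation | 200 × 0.083 = 16.6 | 240 × 0.10 = 24 | 16.6/5 = 3.3 to 24/5 = 4.8 |
| Acute, mortality (no exclusions) | 230 × 0.118 = 27.1 | 276 × 0.12 = 33.1 | 27.1/5 = 5.4 to 33.1/5 = 6.6 |
| Weaning, re-intubation | 150 × 0.083 = 12.5 | 180 × 0.10 = 18 | 12.5/6 = 2.1 to 18/5 = 3.6 |
| Weaning, deaths (assumed rate) | 150 × 0.05 = 7.5 | 180 × 0.10 = 18 | 7.5/6 = 1.25 to 18/5 = 3.6 |

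All lie below 8.9.

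**Simulation of maximum likelihood (ML) against Firth.** There were 1,500 trials per setting. Assumptions not in the documents: age split 40/30/30%, 35% immunosuppressed, covariate log odds ratios 0.3 to 0.5, and a true treatment odds ratio of 0.5, 1 or 2. ML results are for fits without separation.

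- True OR 1: ML geometric mean 0.98–1.05, so no material bias.
- True OR 2, 12 to 28 events: ML 2.09–2.20. True OR 0.5: ML 0.45–0.48.
- On the log scale the smallest excess is 0.737 / 0.693 = 1.06 and the largest 0.808 / 0.693 = 1.17, that is, 6–17% too far from 1.
- The log-OR SD is 0.45–0.74. The bias is therefore about (0.739 − 0.693) / 0.623 = 0.07 to (0.790 − 0.693) / 0.590 = 0.16 of a standard error.
- Firth, over all trials and settings: 1.91–2.04 for a true 2 and 0.48–0.53 for a true 0.5. With about 12 or more events its log-OR SD is about 4–12% smaller than under ML.

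**Separation (any coefficient not finite).**
- Acute models: 0–1.3%.
- Weaning re-intubation: 0.5–7%.
- Weaning deaths at 18 events: 0.2–0.7%.
- Weaning deaths at 7.5 events: 22–28%. A separate run at the assumed 5% rate gave about 17–31%, and a variant with 15% immunosuppressed gave 38%.
- An arm with no events, which leaves the treatment odds ratio itself without a finite estimate: 4–8% at 7.5 events and at most 2% elsewhere.

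**The case against.** A reader might infer that the reported odds ratios will be inflated and that some weaning-phase models will fail to converge. The documents do not support either statement.

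- **Inflation.** ML bias is away from 1, so a protective odds ratio becomes smaller, not larger. At no effect there is none, and the SAP's ventilator-free-days entry in Table 1 says no treatment effect on death is expected. The only formal re-intubation criterion is a non-inferiority margin of 0.10 (D.6.4.1), set beside a 10% rate and so apparently an absolute difference.
- **Inference.** In a simulation at a true OR of 2, ML Wald intervals covered 94.7–95.8% in the acute settings and 96.2% for weaning re-intubation at 10%. Firth gave 95.1–95.7% and 96.2–96.3%.
- **Convergence.** Failure is a risk, not a certainty. It is large only at the 5% floor of a death rate borrowed from another analysis, and there it usually affects a covariate.
- **Existing safeguards.** Fisher's exact test and checks of logistic fit are planned.
- **Timing.** The final SAP follows the unblinded diagnostics described in its May 2024 entry. Changing an estimator now is itself a change after the data were seen.

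Most of this stands and limits the point to an improvement. It does not remove it. The unadjusted test does not replace the adjusted result the SAP requires, and the plan still has no rule for separation. The timing objection is met by labelling the change and showing both results.

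**Conclusion.** The point holds as a modest, optional improvement. The SAP reserves Firth's method for undefined subgroups, while its main re-intubation and mortality models have about 1.25 to 6.6 events per slope against the protocol's own figure of about 9. The gain is removal of a small bias in non-null estimates, slightly better precision, and finite estimates where separation occurs. Nothing here shows that the trial's safety conclusions would be wrong.

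The event counts for re-intubation and acute-comparison mortality rest on the documents' rates and targets, with the 12% mortality figure as a stand-in. The weaning death count rests on an assumed 5–10%. The bias and separation figures rest on the simulation's covariate assumptions, and on oxygenation index being the only added confounder. Further imbalanced covariates would lower the events per slope.

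**What to change.** In the model-fit paragraph and in Table 2 (logistic row), replace the restriction to subgroups with a rule along these lines: *Firth's penalised likelihood, with profile-penalised confidence limits, will be used for any main or subgroup re-intubation or mortality logistic model with fewer than a stated number of events per parameter, and whenever separation occurs.* The threshold could be the protocol's own figure of about 9–10. State the expected events, and say whether immunosuppression enters the weaning-phase models.

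Label the change post hoc and report the Firth result beside the ML result. The cost is a few sentences, a rerun with a method the SAP already cites, and estimates slightly closer to 1.
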